Appendix 7 Immune-Related Response Criteria (cont.)

DETERMINATION OF irBOR

Once a patient has completed all tumor assessments, his/her irBOR may be determined:

Condition	irBOR
At least one irCR	irCR
At least one irPR and no irCR	irPR
At least one irSD and no irCR and no irPR	irSD
At least one irPD and no irCR, no irPR, and no irSD	irPD

irBOR=immune-related best overall response; irCR=immune-related complete response;
irPD=immune-related progressive disease; irPR=immune-related partial response;
irSD=immune-related stable disease.

Appendix 8 Lansky Performance Status Scale

Score	Description
100	Fully active; normal
90	Minor restrictions in physically strenuous activity
80	Active but tires more quickly
70	Both greater restriction of and less time spent in play activity
60	Up and around, but minimal active play; keeps busy with quieter activities
50	Gets dressed, but lies around much of the day; no active play; able to participate in all quiet play and activities
40	Mostly in bed; participates in quiet activities
30	In bed; needs assistance even for quiet play
20	Often sleeping; play entirely limited to very passive activities
10	No play; does not get out of bed

Appendix 9 Karnofsky Performance Status Scale

Score	Description
100	Normal; no complaints; no evidence of disease
90	Able to carry on normal activity; minor signs or symptoms of disease
80	Normal activity with effort; some signs or symptoms of disease
70	Cares for self; unable to carry on normal activity or do active work
60	Requires occasional assistance, but is able to care for most of his/her needs
50	Requires considerable assistance and frequent medical care
40	Disabled; requires special care and assistance
30	Severely disabled; hospitalization indicated; death not imminent
20	Very sick; hospitalization indicated; death not imminent
10	Moribund; fatal processes progressing rapidly

Appendix 10 Recommended Anaphylaxis Management

The following equipment is needed in the event of a suspected anaphylactic reaction during study drug infusion. All equipment and medication must be in the appropriate sizes and doses for the pediatric patients being treated.

- Appropriate monitors (electrocardiogram, blood pressure, pulse oximetry)
- Oxygen and masks for oxygen delivery
- Airway management devices per standard of care
- Epinephrine for intravenous, intramuscular, and/or endotracheal administration in accordance with institutional guidelines
- Antihistamines (oral/IV H1 and H2 antagonists)
- Corticosteroids (IV)
- Albuterol (Salbutamol or equivalent) for bronchospasm
- Intravenous infusion solutions, tubing, catheters, and tape

The following are the procedures to follow in the event of a suspected anaphylactic reaction during study drug infusion:

- Stop the study drug infusion.
- Call for additional assistance!
- Maintain an adequate airway.
- Provide oxygen.
- Ensure IV access ×2 if possible.
- Ensure that appropriate monitoring is in place, with continuous electrocardiogram and pulse oximetry monitoring, if possible.
- Administer epinephrine (1:1000, 0.01 mg/kg intramuscularly [IM]) into lateral thigh, or via route and dose as directed by physician-in-charge). May repeat every 5–15 minutes.
- Administer antihistamines and other medications as required by patient status and directed by the physician in charge.
- Continue to observe the patient and document observations until the patient is transferred to higher-level care.

Appendix 11

Response Assessment in Neuro-Oncology Criteria

Response	Criteria
Complete response	
Requires all of the following:
 
 • Complete disappearance of all enhancing measurable and non-measurable disease sustained for at least 4 weeks • No new lesions • Stable or improved non-enhancing (T2/FLAIR) lesions • Patients must be off corticosteroids (or on physiological replacement doses only) • Clinical status is stable or improved
Partial response	
Requires all of the following:
 
 • $\geq 50\%$ decrease compared with baseline in the sum of products of perpendicular diameters of all measurable enhancing lesions sustained for at least 4 weeks • No progression of non-measurable T1 enhancing disease • No new lesions • Stable or improved non-enhancing (T2/FLAIR) lesions on the same or lower dose of corticosteroids compared to baseline • Clinical status is stable or improved 
Note: Patients with non-measurable disease only cannot have a partial response; the best response possible is stable disease

Stable disease	
Requires all of the following:
 
 • Patient does not qualify for complete response, partial response, or progression • Stable non-enhancing (T2/FLAIR) lesions on same or lower dose of corticosteroids compared to baseline • Clinical status is stable or improved 
Note: In the event that the corticosteroid dose was increased for new symptoms and signs without confirmation of disease progression on neuroimaging, and subsequent follow-up imaging shows that this increase in corticosteroids was required because of disease progression, the last scan considered to show stable disease will be the scan obtained when the corticosteroid dose was equivalent to the baseline dose.

FLAIR = fluid-attenuated inversion recovery.

Note: Adapted from Wen PY, Macdonald DR, Reardon DA, et al. Updated response assessment criteria for high-grade gliomas: response assessment in neuro-oncology working group. *J Clin Oncol* 2012;28:1963–72.

Appendix 11

Response Assessment in Neuro-Oncology Criteria (cont.)

Response	Criteria
Progression	
Defined by any of the following:
 
 • $\geq 25\%$ increase in sum of the products of perpendicular diameters of enhancing lesions compared with the smallest tumor measurement obtained either at baseline (of no decrease) or best response, on a stable or increasing dose of corticosteroids • Significant increase in T2/FLAIR non-enhancing lesions while taking stable or increasing doses of steroids compared with baseline scan or best response after initiation of therapy, not caused by comorbid events (e.g., radiation therapy, demyelination, ischemic injury, seizures, postoperative changes, or other treatment effects) • Presence of any new lesions • Clear clinical deterioration not attributable to other causes apart from the tumor (e.g., seizures, medication adverse effects, complications of therapy, cerebrovascular events, infection, and so on) or decreases in corticosteroid dose • Failure to return for evaluation due to death or deteriorating condition • Clear progression of nonmeasurable disease

FLAIR =fluid-attenuated inversion recovery.

Note: Adapted from Wen PY, Macdonald DR, Reardon DA, et al. Updated response assessment criteria for high-grade gliomas: response assessment in neuro-oncology working group. *J Clin Oncol* 2012;28:1963–72.

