3.4.4 Efficacy Outcome Measures

The primary efficacy outcome measures for this study are as follows:

- Objective response, defined as a complete or partial response for patients with measurable disease or neuroblastoma patients with evaluable disease at baseline, or a complete response for patients with non-measurable but evaluable disease at baseline (except patients with neuroblastoma) on two consecutive occasions ≥ 4 weeks apart, as determined by the investigator using RECIST v1.1 for patients with solid tumors (see [Appendix 6](#)), *m*INRC for patients with neuroblastoma (see [Appendix 3](#)), Revised Response Criteria for Malignant

Lymphoma for patients with Hodgkin's lymphoma or non-Hodgkin's lymphoma (see [Appendix 4](#)), and RANO criteria (see [Appendix 11](#)) for patients with ATRT.

- Clinical benefit response (CBR), defined as objective response or stable disease for at least 6 months, as determined by RECIST v1.1 for patients with osteosarcoma (see [Appendix 6](#))
- PFS, defined as the time from initiation of study drug to the first documented occurrence of progressive disease, as determined by the investigator using RECIST v1.1 for patients with solid tumors (see [Appendix 6](#)), mINRC for patients with neuroblastoma (see [Appendix 3](#)), Revised Response Criteria for Malignant Lymphoma for patients with Hodgkin's lymphoma or non-Hodgkin's lymphoma (see [Appendix 4](#)), and RANO criteria (see [Appendix 11](#)) for patients with ATRT, or death from any cause, whichever occurs first

The secondary efficacy outcome measures for this study are as follows:

- DOR, defined as the time from the first tumor assessment that supports the patient's objective response to the time of progressive disease, as determined by the investigator using RECIST v1.1 for patients with solid tumors (see [Appendix 5](#)), mINRC for patients with neuroblastoma (see [Appendix 3](#)), Revised Response Criteria for Malignant Lymphoma for patients with Hodgkin's lymphoma or non-Hodgkin's lymphoma (see [Appendix 4](#)), and RANO criteria ([Appendix 11](#)) for patients with ATRT, or death from any cause, whichever occurs first
- OS, defined as the time from initiation of study drug to death from any cause

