4.5.5.2 Response Criteria

All tumors will be evaluated for disease response and progressive disease with RECIST v1.1 (see [Appendix 6](#)) with the exception of those listed below.

- Neuroblastoma: *m*INRC (see [Appendix 3](#))
- Hodgkin's lymphoma and non-Hodgkin's lymphoma: Revised Response Criteria for Malignant Lymphoma (see [Appendix 4](#))
- ATRT: RANO criteria (see [Appendix 11](#))

Patients with synchronous ATRT and rhabdoid tumor with no clear primary should be enrolled into the rhabdoid tumor cohort. These patients' tumors will be evaluated with RECIST v1.1 criteria.

Patients who enroll with evaluable but not measurable disease will have a modified response assessment. For such patients, partial response cannot be determined; therefore, response will be limited to complete response, stable disease, or progressive disease.

During treatment, patients who show evidence of clinical benefit will be permitted to continue atezolizumab treatment after criteria for progressive disease for their specified response assessment are met, if they meet all of the following criteria:

- Evidence of clinical benefit as assessed by the investigator and agreed upon by the Medical Monitor
- Absence of symptoms or signs (including worsening laboratory test values) indicating unequivocal progression of disease
- No decline in Lansky or Karnofsky Performance Status that can be attributed to disease progression
- Absence of tumor progression at critical anatomical sites (e.g., leptomeningeal disease) that cannot be managed by protocol-allowed medical interventions

Patients and/or their parents or guardians must sign a consent acknowledging treatment continuation after possible worsening disease in order to continue to receive atezolizumab. Patients for whom radiographic disease progression is confirmed at a subsequent tumor assessment may be considered for continued study treatment at the discretion of the investigator if they have evidence of clinical benefit and continue to meet the criteria above. If an individual patient continues to experience clinical benefit beyond 2 years of radiologic progressive disease (see Section 3.3.4), the Sponsor and treating physician will apply for additional approval from health authorities for continued treatment.

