Non-rhabdomyosarcoma tissue sarcoma	10	10	2
Ewing sarcoma	10	10	2
Rhabdoid tumor	5	6	1
Atypical teratoid rhabdoid tumor	5	6	1

^a Combination therapy.

^b Clinical benefit response: objective response or stable disease for at least 6 months.

Overall, approximately 100 patients will be enrolled in the study.

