6.6.1 Primary Efficacy Endpoint

The primary endpoints for efficacy are ORR and PFS. For patients with measurable disease or patients with neuroblastoma who have evaluable disease at baseline, an objective response is defined as a complete or partial response on two consecutive occasions ≥ 4 weeks apart, as determined by the investigator using RECIST v1.1 for patients with solid tumors (see [Appendix 6](#)), *mINRC* for patients with neuroblastoma (see [Appendix 3](#)), Revised Response Criteria for Malignant Lymphoma for patients with Hodgkin's lymphoma or non-Hodgkin's lymphoma (see [Appendix 4](#)), and *RANO criteria* (see [Appendix 11](#)) for patients with ATRT.

For patients with non-measurable but evaluable disease at baseline (except *patients with neuroblastoma*), an objective response is defined as a complete response on two consecutive occasions ≥ 4 weeks apart, as determined by the investigator using RECIST v1.1 for patients with solid tumors (see [Appendix 6](#)), Revised Response Criteria for Malignant Lymphoma for patients with Hodgkin's lymphoma or non-Hodgkin's lymphoma (see [Appendix 4](#)), and *RANO criteria* (see [Appendix 11](#)) for patients with ATRT.

ORR is the percentage of patients who are determined to have an objective response. Patients with no post-baseline tumor assessments will be counted as non-responders. ORR and corresponding 95% exact CI using the Blyth–Still–Casella method will be summarized overall and by tumor type cohort (except for the osteosarcoma tumor type cohort).

CBR is defined as objective response or stable disease for at least 6 months, as determined by RECIST v1.1 for patients with osteosarcoma (see [Appendix 6](#)). CBRR is the percentage of patients who are determined to have a CBR. Patients with no post-baseline tumor assessments will be counted as not having CBR. CBRR and corresponding 95% CI will be summarized for the osteosarcoma tumor type cohort only.

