A lesion identified during the study in an anatomical location that was not scanned at baseline is considered a new lesion and will indicate disease progression.

If a new lesion is equivocal, for example because of its small size, continued therapy and follow-up evaluation will clarify if it represents truly new disease. If repeat scans confirm there is definitely a new lesion, then progression should be declared using the date of the initial scan.

EVALUATION OF RESPONSE

a. Timepoint Response (Overall Response)

It is assumed that at each protocol-specified timepoint, a response assessment occurs. [Table 1](#) provides a summary of the overall response status calculation at each timepoint for patients who have measurable disease at baseline.

When patients have non-measurable (therefore, non-target) disease only, [Table 2](#) is to be used.

Appendix 6 Response Evaluation Criteria in Solid Tumors: Modified Excerpt from Original Publication (cont.)

**Table 1 Timepoint Response: Patients with Target Lesions
(with or without Non-Target Lesions)**

Target Lesions	Non-Target Lesions	New Lesions	Overall Response
CR	CR	No	CR
CR	Non-CR/non-PD	No	PR
CR	Not evaluated	No	PR
PR	Non-PD or not all evaluated	No	PR
SD	Non-PD or not all evaluated	No	SD
Not all evaluated	Non-PD	No	NE
PD	Any	Yes or no	PD
Any	PD	Yes or no	PD
Any	Any	Yes	PD

CR=complete response; NE=not evaluable; PD=progressive disease;
PR=partial response; SD=stable disease.

**Table 2 Timepoint Response: Patients with Non-Target
Lesions Only**

Non-Target Lesions	New Lesions	Overall Response
CR	No	CR
Non-CR/non-PD	No	Non-CR/non-PD ^a
Not all evaluated	No	NE
Unequivocal PD	Yes or no	PD
Any	Yes	PD

CR=complete response; NE=not evaluable; PD=progressive disease.

^a “Non-CR/non-PD” is preferred over “stable disease” for non-target disease since stable disease is increasingly used as an endpoint for assessment of efficacy in some studies; thus, assigning “stable disease” when no lesions can be measured is not advised.

b. Missing Assessments and Not-Evaluable Designation

When no imaging/measurement is done at all at a particular timepoint, the patient is not evaluable at that timepoint. If only a subset of lesion measurements are made at an assessment, usually the case is also considered not evaluable at that timepoint, unless a

Appendix 6

Response Evaluation Criteria in Solid Tumors: Modified Excerpt from Original Publication (cont.)

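### Appendix 11 caps ATRT patients with non-measurable disease only at stable disease, while Sections 3.4.4, 4.5.5.2 and 6.6.1 allow them a complete response

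*Combined protocol and SAP*

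**What the plan says.** Six places bear on how an ATRT patient with non-measurable disease only is scored.

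- **Appendix 11, note in the partial-response row:** "Patients with non-measurable disease only cannot have a partial response; the best response possible is stable disease".
- **Appendix 11, complete-response row:** "Complete disappearance of all enhancing measurable and non-measurable disease sustained for at least 4 weeks", together with conditions on new lesions, non-enhancing lesions, corticosteroids and clinical status. The row does not exclude patients whose disease is all non-measurable.
- **Appendix 11, stable-disease row, first condition:** "Patient does not qualify for complete response, partial response, or progression".
- **Section 3.4.4** (the synopsis agrees) counts as an objective response "a complete response for patients with non-measurable but evaluable disease at baseline (except patients with neuroblastoma) on two consecutive occasions" at least 4 weeks apart, and names RANO in Appendix 11 as the criteria for ATRT.
- **Section 6.6.1**, for non-measurable but evaluable disease outside neuroblastoma: "an objective response is defined as a complete response on two consecutive occasions", again with RANO in Appendix 11 for ATRT.
- **Section 4.5.5.2**, for patients who enroll with evaluable but not measurable disease: "For such patients, partial response cannot be determined; therefore, response will be limited to complete response, stable disease" or progressive disease. It makes no exception for ATRT.

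Such patients can enroll. Section 4.1.1 accepts disease that is evaluable but not measurable, and Section 4.1.2 does not require ATRT patients to have disease outside the CNS.

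**The concern.** The investigator scores response, and Sections 3.4.4 and 6.6.1 send the investigator to Appendix 11 to do it. The only sentence there that addresses patients with non-measurable disease only sets stable disease as their ceiling. An investigator who follows it records stable disease, and Section 6.6.1 then has no CR to count. An investigator who works from Section 6.6.1, or from the CR row alone, records a CR. No passage says which text prevails.

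At stake are the ORR, which is a primary efficacy endpoint, and the responder count that feeds the ATRT expansion decision. Section 6.6 analyzes all treated patients, so a capped patient stays in the denominator as a non-responder. The same patient would also be left out of duration of response, which is defined only for patients with an objective response.

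**Working it through.** **1. The plan's own rule.** Table 3 lists "Atypical teratoid rhabdoid tumor" with a historical ORR of 5%, a minimum of 6 patients and a minimum of 1 responder for expansion. No alpha, power or target rate is stated, so the rule cannot be derived from stated inputs. Its chance of being met at the historical rate is 1 − 0.95^6 = 1 − 0.735 = 0.265. The same calculation for the other Table 3 rows gives 0.263 to 0.335, so the ATRT row is in line with the table and is not in question. What matters is that the threshold is a single responder.

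**2. Outcomes open to an ATRT patient with non-measurable disease only.**

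| Source | CR | PR | Stable disease | Progression |
|---|---|---|---|---|
| Sections 3.4.4 and 6.6.1, synopsis | counts as objective response if confirmed | does not count | not a response | not a response |
| Section 4.5.5.2 | possible | not possible | possible | possible |
| Appendix 11, CR row | possible, no exclusion | – | – | – |
| Appendix 11, note | barred as written | barred | best possible | possible |

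All the sources agree that PR cannot be a response for these patients. Only CR is in dispute.

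**3. Consistency within Appendix 11.** Take a patient with non-measurable disease only who meets every condition of the CR row. The note bars CR. The stable-disease row bars stable disease, because the patient qualifies for CR. PR is barred by all texts, and the patient has not progressed. Read literally, Appendix 11 leaves this patient without a category.

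**4. Comparison with the RECIST appendix.** Appendix 6 gives a separate Table 2 for the matching case, "When patients have non-measurable (therefore, non-target) disease only", and its first row is CR. The plan's approach for other solid tumors therefore allows CR in non-measurable disease.

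**5. Effect on the ATRT count.** Take 6 treated ATRT patients, one confirmed CR in a patient with non-measurable disease only, and no other responder.

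- Under Section 6.6.1: 1/6 = 16.7%, and 1 ≥ 1, so the threshold is met.
- Under the Appendix 11 note: 0/6 = 0%, and 0 < 1, so the threshold is not met.

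Six is the Table 3 minimum. Section 3.1 speaks of initial assessment after at least 10 patients in a cohort. If 10 were enrolled and the requirement stayed at 1 responder (an assumption), the contrast would be 1/10 = 10% against 0/10, again met against not met.

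**The case against.** The strongest reply is that the note sits in the partial-response row and was meant only to say that, short of a CR, these patients can reach no more than stable disease. On that reading every row of Appendix 11 fits together and agrees with the synopsis and with Sections 3.4.4, 4.5.5.2 and 6.6.1. This is plausible as intent and supports the proposed rewording. It does not remove the problem, because the note contains no such qualification and investigators are directed to this appendix to score.

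A second reply is that the case is rare. It needs non-measurable disease only, sustained disappearance of enhancing disease, no corticosteroids beyond physiological replacement, and stable or improved clinical status. Patients evaluable only by tumor markers may not be scoreable under RANO on either reading. Patients with synchronous ATRT and rhabdoid tumor and no clear primary are scored by RECIST v1.1 in the rhabdoid cohort and are unaffected. All of this stands. The documents give neither the number of such patients nor their CR rate, so no probability of a changed decision is offered here.

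A third reply is that the threshold does not act alone, which is also correct. Section 6.1 plans no formal hypothesis test and lets the initial assessment consider early efficacy signals. Sections 3.1 and 6.1 let expansion weigh other information. Section 3.1.2 says that enrollment may be stopped, and allows extension in a slow-enrolling, rare cohort with strong evidence of efficacy.

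**Conclusion.** The conflict is real and lies in the current text. As written, the note bars a CR that the synopsis, three body sections and the CR row of Appendix 11 all allow. In the worked case a single patient moves the ATRT cohort from 1/6 to 0/6 and across the Table 3 threshold. That case assumes exactly one such responder and no other; it does not claim that this is likely. The practical impact is modest: an inconsistently scored ORR and responder count.

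A reader might infer two stronger conclusions that the documents do not support.

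- **That the note would close the ATRT cohort.** Missing the threshold permits stopping but does not require it, and a confirmed CR could still be weighed under the provisions above.
- **That neuroblastoma has the same conflict.** Section 4.5.5.2 does deny PR in evaluable-only disease, while Section 6.6.1 counts PR in evaluable neuroblastoma. But Appendix 3 treats MIBG-positive and marrow disease as measurable in this study, which largely removes the clash. Its Table 1 allows progression with any CT/MRI status, and its text allows stable disease by marrow or MIBG criteria. What remains is narrower: Appendix 3 gives no overall route to PR or very good partial response for patients without CT/MRI lesions.

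**What to change.** Reword the note in the partial-response row of Appendix 11 to match Section 6.6.1: ATRT patients with non-measurable disease only cannot have PR, but can have CR, stable disease or progression. This is a one-sentence edit. It needs no new assessments, data or response definitions, and leaves the CR and stable-disease rows as they are. Any ATRT patient with non-measurable disease only who has already been scored should be checked against the reworded note.

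Separately, the sponsor should reconcile Appendix 3 with Section 6.6.1 by stating whether and how an overall PR is assigned to neuroblastoma patients without CT/MRI lesions. That takes a sponsor decision and matching wording, with no new assessments.
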